### **13.4 Allocation of Participants to Doses**

#### **13.4.1 The Weighted Dose-Toxicity Model**

Doses will be allocated to patients by means of the Time-to-Event Continual Reassessment Method (TITE-CRM) Phase I trial. A logistic dose-toxicity model was used for this trial with rescaled dose  $d = (\log(p_0 / (1-p_0)) - 3)$ .

$$p(d) = e^{3+ad} / (1 + e^{3+ad}), \text{ (eq. 1)}$$

In the logistic dose-toxicity model, the prior distribution of the dose-toxicity parameter  $\alpha$  is Gaussian with mean 1 and standard deviation of 0.3 which is based upon experience with other trials using this model.  $\alpha=1.0$  represents our initial assumption about the toxicity of treatment, as displayed in the third column of Table 13.1

The weight function reflects the amount of information available from a patient. If a DLT is observed, the full information from this patient is available and the weight will be 1. Otherwise, the uniform weight function ranging from 0 to 12 months will be used. Each patient will be followed for DLT until the patient either reaches one year (12 months) from the start of SBRT without experiencing a DLT or experiences a DLT, whichever comes first. Let the time to a DLT of patient be  $U_i$ , then the weight function,  $w(u) = u/12$ .

This is translated into the following:

- A) Patients who have enrolled in this trial but have not experienced a DLT have a weight equal to the proportion of the 12 months observation period they have completed.
- B) Patients who have experienced a DLT before 12 months from the start of SBRT or complete protocol treatment without a DLT have a full weight, 1.

The goal of the trial is to determine the fraction size (dose) for SBRT most closely associated with a 0.20 probability of a DLT (specified as the *target rate*). As patients present for enrollment, they are assigned the highest dose associated with an estimated probability of a DLT less than or equal to the target rate of 0.2. The initial estimates of the probability of a DLT at each dose (column 3 of Table 13.1) are updated with the accumulated patient information using a Bayesian paradigm so that the estimation of the target dose, and, thereby, the assignment of the next dose, is based upon all the information available at the time of enrollment. To allow the trial to remain open to new patient entries without pause, while using the maximum available information, data from patients who have been enrolled but have not completed the 1 year observation period are weighted according to the proportion of the observation period the patient has completed (data from patients who have experienced a DLT are fully weighted).

**Table 13.1:** Toxicity probability estimates of trial design and simulation assumptions used to determine operating characteristics

Dose Level	SBRT Fraction Dose (Gy)	Probability of Toxicity			
		Design ( $p_0$ )	Scenario		
			DLT per trial design (DLT-td)	DLT+	DLT++
1	8.0	0.01	0.01	0.02	0.02
2	8.5	0.02	0.02	0.04	0.05
3	9.0	0.04	0.04	0.06	0.08
4	9.5	0.05	0.05	0.10	0.13
5	10.0	0.08	0.08	0.15	0.18
6	10.5	0.10	0.10	0.20	0.30
7	11.0	0.14	0.14	0.30	0.40
8	11.5	0.17	0.17	0.35	0.60
9	12.0	0.20	0.20	0.45	0.80

#### 13.4.2 Assignment of Dose

The first patient will be treated at dose Level 5 (10 Gy). Whenever a subsequent patient presents for enrollment, the expected value of  $\alpha$ , conditioned on the prior distribution and the data (weighted, where no DLTs have occurred, by the proportion of the 1 year observation period the patients have completed) will be calculated, from which the expected probability of a DLT at each dose level will be estimated. The patient will be assigned to the highest dose level with an expected probability of a DLT less than or equal to the target rate of 0.20, subject to the following escalation restrictions:

- Dose may only increase one level between consecutive patients;
- Dose may decrease any number of levels between consecutive patients;
- A patient may not be assigned to a next higher dose level unless there is at least 1 year of cumulative observation at the current dose level.

This cumulative observation may be distributed among several patients. Based on the data from RTOG 0236, most toxicity from SBRT occurs within 3 months of treatment. While it is possible that the 1-year cumulative observation may be distributed across many people, it is not expected that the actual distribution will include more than 4 patients, all of whom should have at least 3 months of observation time. The actual number of patients used to reach 1 year

of cumulative observation will be monitored, and appropriate action will be taken, such as not increasing to a new dose level, should the number of patients be deemed too excessive.

Under these rules, it is not possible to state in advance the number of patients who will be treated at each dose, but estimated distributions of dose allocations under several different assumptions about dose-toxicity models are presented in Figure 13.2.

**Note:** Due to technical reasons, a patient assigned to a dose level may actually have been treated at a lower dose level. As soon as this information becomes available, the patient will be analyzed at the lower dose level received prior to any calculations for the next patient's dose assignment in the next patient.

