The distributions of target doses that the trial selects are presented in the right column of Figure 13.1. If the design assumptions about P(DLT) are correct (DLT-td), the trials overwhelmingly pick the correct target dose, indicated by the asterisk (Level 9). If P(DLT) is underestimated as in scenario DLT+ , the target dose is picked within one level of the true target dose (i.e., with  $0.15 \leq P(\text{DLT}) \leq 0.30$ ) in over 90% of the simulated trials. If the P(DLT) is more severely underestimated as in scenario DLT++ , that proportion is higher.

[figure not shown]
**13.2.3** Estimation of Primary Tumor Control (8/20/10)

The average number of patients treated at each dose is displayed in the left column of Figure 13.2. Again, the target dose is denoted by an asterisk. In the DLT-td cases, 7-14 patients are treated at Levels 5-8 due to the starting dose (level 5, 10 Gy) and escalation restrictions. In the DLT+ simulations, 8-14 patients on average are treated on either of the 2 dose levels (8 and 9) with  $P(\text{DLT}) > 0.3$ , which result, on average in 3-5 DLTs. In the DLT++ simulations, 8-15 patients on average are treated on 1 of 3 dose levels (7, 8, and 9) with  $P(\text{DLT}) > 0.3$  which result on average in 4-8 DLTs.

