Patients who complete protocol treatment but cannot be observed for a DLT for 1 year (e.g., due to death from other than toxicity or patient refusal) will not count towards the accrual goal, but their data will be used to allocate doses to subsequent patients and in the final analyses for toxicity, primary tumor control and survival, they will be weighted, as appropriate, by the proportion of the observation period they have completed. Note: Patients, who have experienced a DLT, are fully weighted.

It is anticipated that average accrual will be 2 patients per month. Based upon RTOG 0236 (another RTOG trial utilizing SBRT), it is projected that 80% of patient entries will be evaluable for DLT analysis. So to accrue 75 evaluable patients, a total of **94 patients** will have to be entered, and this will take 4 years to complete.

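### Section 13.4.2 expects at most 4 patients, each with 3 months, behind every escalation, but the escalation rule does not require this and planned accrual does not produce it

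*Protocol*

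**What the plan says.** Section 13.4.2 lists three escalation restrictions. The third bars a move to the next level "unless there is at least 1 year of cumulative observation at the current dose level". The text below the list lets that year be pooled over several patients and concedes that it might be spread over many. It then gives the expectation: "it is not expected that the actual distribution will include more than 4 patients, all of whom should have at least 3 months" of observation. A check follows. "The actual number of patients used to reach 1 year" will be monitored, and escalation may be withheld "should the number of patients be deemed too excessive". No number is attached to that check, and the text does not say which patients are counted.

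Two other statements fix the pace. Section 13.3 says "It is anticipated that average accrual will be 2 patients per month", and Section 5.1 says that accrual is not suspended while a dose level is assessed. Section 6.0 has treatment start 1 to 3 weeks after registration, while DLT observation runs from the start of SBRT.

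**The concern.** The expectation reads as an assurance that a dose is raised only on patients who have each passed 3 months. The rule asks only for a total, and many short follow-ups can supply it when patients keep entering. This matters because Section 1.3 regards toxicity to central structures as more likely between 1 and 6 months, or later, than within the first month. If the assurance does not hold, investigators and safety reviewers are told of a protection that the rule does not give. The person applying the discretionary check also has an expected count that planned accrual will usually exceed.

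**Working it through.** **Inputs.** Accrual 2 per month, so one entry every 0.5 month (Section 13.3); no pause (Section 5.1); 12 patient-months needed at the current level (Section 13.4.2); SBRT start 1 to 3 weeks after registration (Section 6.0). Assumed: no DLT on the level, and every entry goes to the current level. The accrual plan is consistent: 75/0.80 = 94 entries, and 94/2 = 47 months, about 4 years.

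**Where the stated figure can come from.** 4 × 3 = 12. With even entries, suppose only patients at 3 months or more are counted.
- Month 4.0: 4.0 + 3.5 + 3.0 = 10.5, not enough.
- Month 4.5: 4.5 + 4.0 + 3.5 + 3.0 = 15.0, from exactly 4 patients.

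So the expectation follows under that counting convention.

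**What the rule as written gives.** With n patients on the level and entries at rate r, cumulative observation when the next patient registers is n(n+1)/(2r). At r = 2:
- n = 6: 6 × 7/4 = 10.5 months, not enough.
- n = 7: 7 × 8/4 = 14.0 months, at month 3.5.

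The seven then have 3.5, 3.0, 2.5, 2.0, 1.5, 1.0 and 0.5 months. The mean is 14.0/7 = 2.0, and 2 of 7 are at 3 months.

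**Delay from registration to SBRT (even entries).**

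| Delay | Patients on level | Total months | At 3 months or more |
|---|---|---|---|
| none | 7 | 14.0 | 2 |
| 1 week | 7 | 12.39 | 1 |
| 2 weeks | 8 | 14.32 | 2 |
| 3 weeks | 8 | 12.67 | 1 |

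**Counting only the longest-followed patients needed.** With no delay, 3.5 + 3.0 + 2.5 + 2.0 = 11.0, and adding 1.5 gives 12.5: 5 patients, the fifth at 1.5 months. A 2-week delay also gives 5: 3.54 + 3.04 + 2.54 + 2.04 + 1.54 = 12.70. A 1-week delay gives 6: 3.27 + 2.77 + 2.27 + 1.77 + 1.27 = 11.35, and adding 0.77 gives 12.12. A 3-week delay also gives 6: 3.31 + 2.81 + 2.31 + 1.81 + 1.31 = 11.55, and adding 0.81 gives 12.36.

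**Random entries (Poisson, 2 per month, simulated).**
- Everyone on the level: median 7 (5th to 95th percentile 5 to 10), or 8 (5 to 11) with a half-month delay. At most 4 patients, all at 3 months or more: 0.4% of runs, or 0.1% with the delay.
- Fewest patients reaching 12 months: median 5 (3 to 8). At most 4 in 35% of runs; at most 4 and all at 3 months or more in about 12%.

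**Does the model hold the dose back instead?** Patients receive "they are assigned the highest dose associated with an estimated probability of a DLT less than or equal to the target rate of 0.2". The design value at Level 9 in Table 13.1 is already 0.20. After the seven DLT-free follow-ups above at Level 5, the posterior mean of the dose-toxicity parameter is 1.05 and Level 9 stands at 0.167. Without a DLT, the 1-year restriction is what binds.

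**The case against.** **The count is ambiguous, so the arithmetic may not be wrong.** The expectation concerns patients used to reach the year, not everyone on the level, and 4 × 3 suggests that the authors meant patients past 3 months. This is fair. The 7 to 8 figure alone would overstate the gap, and the like-for-like count is 5 or 6. But the restriction does not exclude shorter follow-up. As written it permits escalation at month 3.5, not 4.5.

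**Accrual is an average.** Sites must be credentialed, so early entry may be slower. At an even 1 per month with no delay, 5 + 4 + 3 = 12 comes from 3 patients, all at 3 months, and the expectation then holds on the longest-followed count. This stands as a sensitivity. With random entries at that rate, however, at most 4 patients all at 3 months occurs in 45% of runs on that count and 9% when all are counted. At that pace 94 entries would take 94 months, not 47.

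**The wording is hedged and there are other protections.** The text foresees wider spread and names an action. TITE-CRM down-weights short follow-up, Section 13.2 simulates late DLTs, and the safety board meets twice a year. All of this stands and limits the severity. The check has no threshold, though, so it does not make the stated property true.

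**Stronger readings that the documents do not support.** A reader might conclude that "most toxicity from SBRT occurs within 3 months of treatment" is refuted by Appendix VII, where RTOG 0236 shows 2 DLTs in months 0 to 3 and 2 in months 6 to 9. Those are only 4 events, limited to DLTs as this protocol defines them, while the sentence speaks of toxicity generally. A reader might also take "7-14 patients are treated at Levels 5-8 due to the starting dose (level 5, 10 Gy) and escalation restrictions" in Section 13.2.3 as proof. Those are average totals treated, which can include patients entered after a de-escalation or held by the model. They are not counts at first escalation.

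**Conclusion.** The expectation and the rule do not match. At planned accrual the rule is met with 7 to 8 patients on the level, 1 or 2 of them at 3 months, or with 5 or 6 on the count most favourable to the text. This rests on 2 entries per month throughout, even or Poisson spacing, and no DLT on the level. The protocol does not say how a patient with a DLT counts toward the year.

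The point goes no further. A reader might infer that 4 is a limit being breached, that it is the threshold for the monitoring check, or that the sample size or the operating characteristics are wrong. The text gives an expectation, not a limit, and sets no threshold. No sample size or reported simulation depends on the figure. It is a modest mismatch worth correcting, because it describes a safety feature of dose escalation.

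**What to change.** **Preferred.** Amend the third restriction so that only patients with at least 3 months of observation at the current level count toward the 1 year. Any 4 such patients supply at least 12 months, so the stated expectation becomes true by construction. State also how a patient with a DLT is counted.

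Cost with even entries: each escalation moves from month 3.5 to 4.5 and from 7 to 9 patients on the level. Over the four escalations from Level 5 to Level 9 that is 4 × 1 = 4 months and 4 × 2 = 8 patients. These are patients treated at lower levels first, not additions to the 94. With Poisson entries, a slightly stricter rule that requires 4 patients at 3 months moves the means from 3.64 to 5.00 months and from 7.3 to 10.0 patients. That bounds the cost at about 4 × 1.36 = 5.4 months and 4 × 2.7 = 10.8 patients. Rerun the existing simulations with the amended rule.

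**If the rule stays as it is.** Replace the expectation with what the rule gives at 2 per month: about 7 to 8 patients on the level, 1 or 2 at 3 months or more, and about 5 on the longest-followed count. State these assumptions, and say which patients are counted for the monitoring check. This costs wording only.

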### **13.5 Analysis Plan**

#### **13.5.1 Analysis of the Primary Endpoints (8/20/10)**

All patients evaluable per Section 13.3 will be used in the DLT analysis (the primary endpoint of the phase I portion), which will be performed after they have been potentially followed for the 1 year observation period. The patients treated at the MTD of SBRT will be used to estimate the 2-year primary tumor control rate (the primary endpoint of the phase II portion), which will be performed after they have been potentially followed for 2 years. Patients not evaluable will be reported separately. For each such patient, the reason for exclusion, protocol treatment received, and toxicities reported during the first year will be listed.

#### **13.5.1.1 Analysis of Dose-limiting Toxicities (7/27/10)**

The maximal tolerated dose (MTD) of SBRT radiation associated with a 0.20 probability of dose-limiting toxicity (DLT) will be determined as that dose having P(DLT) closest to the target rate of 0.20. DLT is defined as any grade 3 or worse toxicity (per CTCAE, v. 4, MedDRA, v. 12.0), that occurs within 1 year from the start of SBRT, is possibly, probably, or definitely related to treatment, and is related to the specific symptoms in Section 13.1.1). Markov Chain Monte Carlo will be used to estimate the probability of DLT at each dose, along with 95% posterior intervals, using the logistic dose-toxicity model (eg 1) described in Section 13.5.1. The observed proportion of patients experiencing a DLT will be calculated. The distribution of all toxicities will be tabulated by grade and category, as well as the following information:

- I) Analysis by Assigned Dose Level
  - a. Total number of patients assigned to that dose level
  - b. Number of patients who received the assigned dose level
    - i. Number of patients still in treatment
    - ii. Number of patients not evaluable for DLT analysis
    - iii. Number of patients evaluable for DLT analysis
      1. Number of patients who experienced a DLT
      2. Number of patients still at risk for a DLT
      3. Number of patients who completed the risk interval without a DLT
  - c. Number of patients who did not receive the assigned dose level but who received a lower dose level
    - i. Number of patients still in treatment
    - ii. Number of patients not evaluable for DLT analysis
    - iii. Number of patients evaluable for DLT analysis
      1. Number of patients who experienced a DLT
      2. Number of patients still at risk for a DLT
      3. Number of patients who completed the risk interval without a DLT
- II) Analysis by Actual Dose Delivered
  - a. Number of patients still in treatment
  - b. Number of patients not evaluable for DLT analysis
  - c. Number of patients evaluable for DLT analysis
    - i. Number of patients who experienced a DLT
    - ii. Number of patients still at risk for a DLT
    - iii. Number of patients who completed the risk interval without a DLT

In addition, for those patients who did not receive the assigned dose level, the following information will be reported:

1. Dose level actually received
2. Assigned dose level

3. Reason for dose modification

**13.5.1.2** 2-year Primary Tumor Control Rate at MTD (8/20/10)

Primary tumor control is the absence of local progression (defined as local enlargement confirmed by PET or biopsy which occurs within 2 years from the start of treatment). Marginal failures, which are mentioned in Section 11.3.3, will be considered events for local progression. Distant metastases from the index lung cancer or a second primary tumor are not considered local progression. Patients who die with lung cancer but no documented local progression will be considered non-failures and will be censored on the day of their death. Patients who die without progressive lung disease and have no documented local progression will be considered non-failures and will be censored on the day of their death. Cumulative incidence method will be used to estimate the 2-year primary tumor control rate at the MTD of SBRT. Using this confidence interval, the null hypothesis that the probability of 2-year primary tumor control at the selected target dose (MTD) is 0.7 or less will be tested. Ninety percent confidence interval for the probability of response will be constructed by bootstrapping.

**13.5.2** Analysis of Secondary Survival Endpoints

**13.5.2.1** Progression-Free Survival and Overall Survival (8/20/10)

The same patients used for DLT analysis will be used in these analyses, which will be performed after they have been potentially followed for 2 years. The failure event for progression-free survival (PFS) is defined as the first occurrence of local and/or regional disease progression, distant metastases, second primary tumor, or death due to any cause. Time to PFS is measured from the date of randomization to the date of the failure event for PFS. Overall survival (OS) time is measured from the date of randomization to the date of death due to any cause.

Kaplan-Meier estimation will be used to calculate OS and PFS rate at each radiation dose level. Cox proportional hazards regression will be used to characterize PFS and OS as a function of dose. As in the analysis of 2-year primary tumor control, possible confounding baseline demographic or clinical variables will be included in the regression model if there is evidence of significant imbalance between doses.

**13.5.2.2** Local Progression, Regional Failure, and Distant Metastases

The same patients for DLT analysis will be used in these analyses, which will be performed after they have been potentially followed for 2 years.

The failure event for local progression (LP) is defined as local enlargement confirmed by PET or biopsy or a marginal failure per Section 11.3.3. The failure event for regional failure (RF) is defined as the first appearance of regional nodal disease. The failure event for distant metastases (DM) is defined as the first appearance of a distant metastases. The time to failure for these secondary endpoints (LP, RF, and DM) will be measured from the date of randomization to the date of the failure event.

The cumulative incidence method will be used to estimate the rates of each endpoint. The treatment effect on these failures may impact the observable measures of outcomes, and other competing risks may dilute the sensitivity. Therefore, Fine and Gray's proportional hazards regression will be used to characterize LP, RF, and DM as a function of dose. Possible confounding baseline demographic or clinical variables will be included in the regression model if there is evidence of significant imbalance between doses.

**13.5.3** Analysis of Secondary Toxicity Endpoints

**13.5.3.1** Any Grade 3 or Worse Toxicity Other Than a DLT Occurring Within the First Year (7/27/10)

This endpoint is defined as any grade 3 or worse toxicity (per CTCAE, v. 4) other than a DLT **occurring within the first year** that is possibly, probably, or definitely related to treatment and occurs within 1 year from the start of SBRT. The distribution of this toxicity will be tabulated by grade and category for each assigned dose level and actual dose received. If the number of applicable toxicities is adequate for analysis, logistic regression will be used to model the distribution of acute adverse events with and without adjustment for demographic or clinical variables.

**13.5.3.2** Late Grade 3 or Worse Toxicity (7/27/10)

This endpoint is defined as any grade 3 or worse toxicity (per CTCAE, v. 4) that is possibly, probably or definitely related to treatment and **occurs after 1 year** from start of SBRT. The distribution of this toxicity will be tabulated by grade and category for each assigned dose

level and actual dose received. If the number of applicable toxicities is adequate for analysis, logistic regression will be used to model the distribution of acute adverse events with and without adjustment for demographic or clinical variables.

The time to late grade 3 or worse toxicity will be measured from the time protocol treatment starts to the time of the worst late grade 3 or worse toxicity after 1 year from start of SBRT. If no such late toxicity is observed until the time of the analysis, the patient will be censored at the time of the analysis. Death without late grade 3 toxicity will be considered as the competing risk for the events and the distribution of time to late grade 3 or worse toxicity will be estimated using the cumulative incidence method.

**13.5.4** Analysis of Tertiary Endpoints (Correlative Studies)

The results from the analyses of tertiary endpoints (Section 13.1.4) will not provide definitive answers to any related research questions. In some instances, the questions concerning the medical physics endpoints of tumor motion and inter-fraction (setup) errors have not yet been clearly defined. Rather, these results will be considered exploratory to generate future hypotheses, for the following reasons: First, the study was not statistically powered for any tertiary endpoint, and secondly, patient participation in submission of specimens for study of the molecular marker is not mandatory in this trial.

The incidence rate of the local progression rate at 2 years will be analyzed with respect to molecular markers (proteomic or genomic) in the blood circulation. They are collected at baseline, during the course of treatment (between the third and fourth dose of SBRT), and at the first follow-up after SBRT. The time to first reported occurrence of grade  $\geq 2$  pulmonary adverse events and the first reported occurrence of grade  $\geq 2$  non-pulmonary adverse events will be separately analyzed with respect to molecular markers. The logistic and the proportional hazard regression models could be utilized to adjust for other possible confounding covariates.

**13.5.5** Interim Reporting

Interim reports will be prepared every 6 months until the initial manuscript reporting the treatment results has been submitted. The usual components of this report are:

- a. the patient accrual rate with a projected completion date for the accrual phase;
- b. accrual by institution;
- c. the distribution of pretreatment characteristics;
- d. the frequency and severity of the toxicities.

To monitor the safety of this study, it will be officially reviewed by the RTOG Data Safety Monitoring Board for Phase I and II studies twice a year in conjunction with the RTOG semi-annual meeting and on an “as needed” basis between RTOG meetings.

**13.5.6** Clinical Data Update System (CDUS) Monitoring

This study will be monitored by the Clinical Data Update System (CDUS) version 3.0. Cumulative CDUS data will be submitted quarterly by electronic means. Reports are due January 31, April 30, July 31, and October 31.

**13.5.7** Reporting DLT analysis

This analysis will occur after all evaluable patients have been potentially observed for 1 year. The report will include:

- a. all cases entered into the trial; exclusions with reasons;
- b. institutional accrual;
- c. distribution of important prognostic baseline variables;
- d. observed results for the endpoints listed in Sections 13.1.1, 13.1.4, and 13.1.5.

**13.5.8** Reporting 2-year Primary Tumor Control Analysis (8/20/10)

This analysis will occur after all evaluable patients have the necessary follow-up to estimate 2-year primary tumor control rate per dose level. The progression free survival and the overall survival will be also analyzed. The report will include:

- a. all cases entered into the trial; exclusions with reasons;
- b. institutional accrual;
- c. distribution of important prognostic baseline variables;
- d. observed results for the endpoints listed in Sections 13.1.2, 13.1.3, and 13.1.5.

